9.4.5 Cost-effectiveness of Treatment Regimens

The cost-effectiveness analysis will be conducted from a payer perspective and will be expressed as incremental cost required to produce one additional unit of quality-adjusted life year (QALY). Data on each participant's use of medical and non-medical resources related to urologic or gynecologic conditions will be collected during the follow up period. Direct and indirect costs of the treatment of apical pelvic organ prolapse with native tissue surgical repair or transvaginal mesh repair and women's preference for health states for improvement in pelvic organ prolapse will be estimated.

We plan to capture incremental health care resource use related to study interventions and complications and other prolapse management (such as pessary use or additional surgery). Costs will be estimated using the resource costing method where medical service use from each study case report form is monetized by multiplying the number of units of each medical service by the average unit cost of this service in dollars. This method allows a consistent capture of resource use when costs are incurred across multiple health systems or payers. Detailed case report forms, that include the procedures performed (e.g. surgical interventions) and clinical events (e.g. complications, readmissions) will be completed by the study coordinator at study visits. Data from three resource types (physician visits, hospital procedures and admissions, and emergency room visits) will be collected. Cost for each medical service use will be assigned based on national Medicare

reimbursement rates, as indicated in the table below. Additionally, we will obtain detailed billing records for a limited number of procedures and hospitalizations in selected study sites (e.g. prolonged admission to the ICU or readmission to the hospital for a surgical complication).

Service	Price Weight
Physician visit	Medicare reimbursement
Surgical intervention and admission	Medicare reimbursement
Complication hospitalization - routine	Medicare reimbursement
Complication hospitalization – significant	Billing record – actual amount paid
ER – routine complication	Medicare reimbursement
ER – significant complication	Billing record – actual amount paid
Subsequent surgery	Medicare reimbursement

The SF-6D preference-based utility index algorithm derived from the SF-12 instrument53 will be used to calculate each participant's utility index at baseline and various follow up time points based on her responses to the SF-12 questionnaire. The SF-6D focuses on seven of the eight health domains covered by the SF-12: physical functioning, role participation (combined role-physical and role-emotional), social functioning, bodily pain, mental health, and vitality.). This instrument has been previously used in women with urinary incontinence54. These data will be used to compare change in QALYs between the two treatment groups. We are choosing to use a general scale to calculate change in utilities (rather than condition-specific) to allow for comparison of cost-effectiveness results with other interventions and diseases. Because the follow up period for participants spans at least three years, costs and QALYs in the second year and third year of follow up will be discounted using a 3% discount rate/year.

Differential mean costs and differential mean QALYs between the two treatment groups will be estimated using multiple regression analysis. Specifically, a generalized linear model with appropriate link function (e.g., log-link) and response probability distribution (e.g., gamma distribution) will be used to analyze costs due to the potential skewness and heteroscedasticity of medical expenditure data, while an ordinary least squares regression will be used for analyzing QALY data. The models will account for treatment group, study site and stratification factors, as well as other characteristics of the participants that are found to differ significantly between the traditional vaginal hysterectomy with native tissue vault suspension and mesh hysteropexy suspension groups. When estimating QALYs, we will also adjust for participants' baseline utility scores to account for potential imbalance in baseline utility between the two treatment groups.55

We will calculate the incremental cost-effectiveness ratio (ICER), which is the differential mean costs divided by the differential mean QALYs between the two groups, to assess the additional costs associated with each additional QALY gained. Our base case analysis will be conducted based on participants with complete data. Sensitivity analysis will be conducted to include participants with incomplete data using the multiple imputation method. Non-parametric bootstrapping resampling technique will be used to derive the 95% confidence interval for the ICER. In addition, cost-effectiveness acceptability curve (CEAC) will be generated to illustrate the likelihood that one treatment is more cost-effective than the other with various ceiling cost-effectiveness ratios.

In the case that a statistically significant difference in changes in utilities (as measured by SF-6D) between the treatment groups is not detected, we plan to conduct supplemental analyses using alternative outcome measures, such as incremental cost per treatment success, incremental cost per POP HRQOL, or incremental cost per satisfaction.

The cost-effectiveness evaluations will be conducted as within-trial comparisons. A decision analytic model will also be developed from trial data to evaluate the trajectory of the cost-effectiveness ratio over a lifetime; assuming an average life expectancy, given the average age of participants at the time of the intervention.

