220	0.94	0.98	0.99	>0.99			
240	0.96	0.98	0.99	>0.99			
260	0.95	0.99	0.99	>0.99			
280	0.98	0.99	>0.99	>0.99			
300	0.98	0.99	>0.99	>0.99			

Based on these calculations, a total of 180 participants will be randomized at a 1:1 ratio to the two treatment arms. This sample size will provide a power of 0.89 to detect an additive difference of 10% in the 2-year success rate (i.e. a hazard ration 0f 0.472) and a power of 0.99 to detect additive differences of 11% or greater in the 2-year success rate (hazard ratios of 0.423 or less).

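### The plan puts a bootstrap 95% interval on the ICER with no rule for resampled QALY differences on both sides of zero; a net-monetary-benefit interval should be added.

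*SAP*

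**What the plan says.** SAP 9.4.5 defines the ICER as a ratio, "which is the differential mean costs divided by the differential mean QALYs between the two groups", and attaches an interval to it: "Non-parametric bootstrapping resampling technique will be used to derive the 95% confidence interval for the ICER". The type of bootstrap interval (percentile, bias-corrected, reordered by quadrant) is not given in the text. Protocol section M.2, Secondary Aim 4, has the same plan and cites two sources for the method.

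The SAP also provides for a weak denominator: "In the case that a statistically significant difference in changes in utilities (as measured by SF-6D) between the treatment groups is not detected", it will add analyses such as "incremental cost per treatment success, incremental cost per POP HRQOL, or incremental cost per satisfaction". These are again costs per unit of effect.

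A second summary of uncertainty is planned: a "cost-effectiveness acceptability curve (CEAC) will be generated to illustrate the likelihood that one treatment is more cost-effective than the other", "with various ceiling cost-effectiveness ratios". No ceiling value is given, and no net-benefit estimate or interval is planned.

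On the population: "Our base case analysis will be conducted based on participants with complete data". Section 6 plans for 180 women, and the display shells in SAP section 17 carry 88 hysteropexy and 87 hysterectomy participants.

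**The concern.** A ratio misbehaves when its denominator can change sign. As the resampled QALY difference passes through zero, the ICER jumps from a very large positive to a very large negative value. The sign also stops being informative. A positive ICER may mean dearer and better, or cheaper and worse. A negative one may mean that mesh hysteropexy dominates or is dominated. Sorting such ratios and reading off the 2.5th and 97.5th percentiles puts values with opposite meanings on one scale.

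This is a realistic case. Protocol section P.1 anticipates similar recovery and morbidity in the two arms, the sample is modest for a QALY comparison, and the SAP has a branch for a non-significant utility difference. That branch leads to further ratios, so the difficulty can recur. At stake is whether the interval reported with the ICER can be read at all.

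**Working it through.** The documents give no QALY difference, QALY SD, cost SD, threshold or power for this aim, so there is no stated figure to reproduce. Everything below except the arm sizes is an assumption.

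**1. How often resamples have the wrong sign.**

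- Arm sizes: 88 and 87 (display shells).
- Assumed 3-year QALY SD: 0.2 to 0.4. Assumed true difference d: 0.02 to 0.05.
- SE = SD × √(1/88 + 1/87) = SD × 0.1512, so 0.0302 at SD 0.2 and 0.0605 at SD 0.4.
- Resamples centre on the observed difference, which itself varies about d. The variance of a resampled difference about d is therefore 2 × SE², and the expected share with the opposite sign is Φ(−d / (SE√2)).

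| SD | d | d/(SE√2) | Expected share of wrong-sign resamples |
|---|---|---|---|
| 0.2 | 0.05 | 1.169 | 12% |
| 0.2 | 0.02 | 0.468 | 32% |
| 0.4 | 0.05 | 0.585 | 28% |
| 0.4 | 0.02 | 0.234 | 41% |

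The simpler Φ(−d/SE), 5% to 37% over the same corners, is the chance that the trial's point estimate has the wrong sign. It is not the share of resamples.

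**2. When a finite interval exists.** The Fieller 95% set for a ratio is a finite interval only if |QALY difference| / SE exceeds 1.96. This is nearly the SAP's own trigger, which is worded on changes in utilities. Below that point a percentile bootstrap still returns finite limits.

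**3. Simulated coverage.** Assumptions: 88/87 women, 600 trials with 600 resamples each, percentile limits, unadjusted means, QALY SD 0.30, gamma costs with SD $8,000, cost–QALY correlation −0.2. Nominal coverage is 95%.

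| True QALY difference | ICER interval coverage at a cost difference of $500 / $2,000 / $5,000 |
|---|---|
| 0 | ICER undefined |
| 0.001 | 17% / 0.5% / 0% |
| 0.005 | 89% / 58% / 58% |
| 0.01 | 95% / 83% / 85% |
| 0.03 | 98% / 96% / 96% |
| 0.1 | 98% / 96% / 97% |
| 0.2 | 94% / 95% / 94% |

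Call a trial straddling if more than 2.5% of its resampled QALY differences lie on each side of zero. For true differences of 0 to 0.01, 93% to 96% of trials straddled, and the median interval was about $630,000 to $2.5 million per QALY wide. At 0.03, 89% to 91% still straddled although coverage was near nominal. Unreadable limits are thus a wider problem than lost coverage.

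**4. The alternative.** Net monetary benefit is threshold × QALY difference − cost difference. At assumed thresholds of $50,000 and $100,000 per QALY, its bootstrap 95% interval covered 92.5% to 96.3% of the time in all 21 scenarios, and 93.0% to 95.2% when the true QALY difference was exactly zero.

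**The case against.** A reader might infer that the SAP expects a zero QALY difference and that its interval is therefore invalid in the likely case. The documents do not support this. The SAP provides for a utility difference that is not significant; it neither predicts one nor equates it with zero. Non-significance alone does not destroy coverage either. At a true difference of 0.03 about 90% of simulated trials were non-significant, yet coverage was 96% to 98%. It falls well short only at about 0.005 and below, with some shortfall at 0.01.

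Three further points have force:

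- The acceptability curve is the probability, at each ceiling, that net benefit is positive. It is unaffected by a zero denominator, so part of the remedy is already planned. It does not give the size of the net benefit or an interval for it.
- The bootstrap variant is not named, and the protocol's cited sources are not available here. The fair criticism is the missing rule. It would be wrong to assume that percentiles will be used.
- SAP 7.7 treats all secondary analyses as exploratory, with descriptive intervals. Nothing in the plan makes this interval the main result for the aim.

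The SE above is also approximate. The planned adjustment for baseline utility would lower it, and restriction to complete cases would raise it.

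**Conclusion.** The point holds in limited form. The plan attaches an interval to a ratio without saying how it is formed or reported when resampled QALY differences straddle zero, and its fallback measures share the weakness. Under the assumed SD of 0.2 to 0.4 and true difference of 0.02 to 0.05 QALY, an expected 12% to 41% of resamples have the wrong sign, enough to make ordered limits mix quadrants. Loss of coverage is confined to true differences at or very near zero, given the assumed SDs and costs.

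Severity is low. The aim is secondary, its intervals are descriptive, and the acceptability curve already gives one sound summary. A net-benefit interval is nonetheless a specific and better method available from the same resamples.

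**What to change.** In SAP 9.4.5:

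- Add incremental net monetary benefit with a bootstrap 95% interval from the same resamples, over a range of thresholds stated in advance and shared with the acceptability curve.
- Show the resamples on the cost-effectiveness plane and keep the acceptability curve.
- Always report the cost and QALY differences with their intervals, and the ICER point estimate.
- Give an ICER interval, with its method named, only when the QALY-difference interval excludes zero. Otherwise state that no finite ICER interval exists.
- Apply the same rule to the fallback cost-per-effect ratios.

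Removing the ICER interval altogether would go too far, because it behaves well when the QALY difference is clearly away from zero. The reporting rule has a limit of its own. At a true difference of 0.03, the simulated ICER interval covered only 55% to 86% of the time among trials with a significant QALY difference, against 94% to 96% at 0.1. The net-benefit interval should therefore be reported in every case.

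The cost is wording, with no new data or resampling. The sponsor must choose thresholds in advance, since the documents give none, and Protocol section M.2 (Secondary Aim 4) needs the same change.

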9.4.6 Changes in Body Image

Total BIS scores will be calculated as described by Hopwood et al, and changes in BIS scores will be correlated with changes in PISQ R scores, the leading edge of prolapse, and POPDI scores using Pearson's and Spearman correlation coefficients. If measures are correlated, we will further describe changes in individual items of the BIS scale before and after treatment for prolapse, to determine which portions of the BIS scale explain the overall change in BIS scores, and evaluate the associations between BIS item scores and PISQ IR item scores. General linear model analyses will be used to evaluate how well the combination of BIS scores, demographic and experimental variables explain changes in PISQ R scores.

Between randomization group comparisons will also be made using linear models for total and item scores controlling for randomization strata. We will also utilize extensions of this model to evaluate if any differences in BIS scores are either modified by or confounded with differences in either efficacy or side effects.

10 SAFETY ANALYSES

10.1 Overview of Safety Analysis Methods

All safety analyses will be performed using the SAF population unless otherwise specified. Study arm summaries will be constructed across all study sites. Descriptive p-values comparing the study arms will be provided on most safety table summaries and will be obtained using Fisher exact tests if the occurrence of such events is rare and Cochrane-Mantel-Haenszel tests for more common events.

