2 PURPOSE OF THE ANALYSES

This statistical analysis plan (SAP) contains detailed information about statistical analyses to be performed to assess the efficacy and safety of vaginal hysterectomy with native tissue vault suspension and mesh hysteropexy suspension in women experiencing uterovaginal prolapse. The results of these analyses will be included in the primary manuscript and a series of pre-planned secondary manuscripts and be provided to Boston Scientific Corporation for a report on the efficacy and safety of mesh-associated surgery required by the FDA under a 522 letter request. Added exploratory analyses may be performed to support further manuscript development. These analyses will not require an update to the SAP.

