3.1.2 Secondary Objectives

The secondary aims for the SUPeR study, which will be addressed through specific planned secondary analyses and associated hypothesis tests and treatment effect estimates, are:

- 1. Secondary Efficacy Outcomes: To compare detailed anatomic and comprehensive functional outcomes (including prolapse, urinary, sexual, bowel and health related quality of life (HRQOL) in both groups.
- 2. Safety: To measure and compare safety, adverse events (including mesh erosion and exposure), pain, and need for subsequent procedures in both groups.
- 3. Predictors of poor outcomes: To determine if advanced prolapse, age, obesity, smoking, menopausal status, estrogens, previous prolapse surgery, and physical activity levels, alone or in combination, predict higher treatment failure.
- 4. Cost- effectiveness: To compare the cost effectiveness of the two surgical approaches and relate the difference in cost of care between the two groups to differences in health utilities and health–related quality of life.
- 5. Body image: To describe changes in body image as measured by a validated scale, the Body Image Scale (BIS). in a group of women undergoing mesh augmented hysteropexy or vaginal hysterectomy and to evaluate whether or not changes in sexual function are associated with changes in body image.

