7.7 Multiple Comparisons and Multiplicity

There is only one formal hypothesis test for this study. As such, a statistical test will be conducted at a 5% type I error rate (two-sided) for the primary efficacy measure, and no adjustments for multiplicity other than control for the single interim analysis will be made. All analyses of secondary outcomes are exploratory in nature; therefore, p-values and confidence intervals are provided for descriptive purposes only. All p-values provided for any baseline and demographic characteristics and safety parameters will be for descriptive purposes only. As such, unless otherwise specified, p-values presented will be on a per analysis basis, with no further control for multiple tests.

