10.2 Adverse Events

As described in Section 3.2, four types of measures will be utilized to characterize participant safety and tolerability measures. First, as a part of the inter-operative and peri-operative data collection forms, information will be collected on surgical complications that characterize the risk and tolerability of the procedure itself. Second, participants will be asked about specific targeted complications on both the post-operative visit and a standard study evaluation collected at 6-month intervals (with those complications automatically populating the AE form. Third, participants will be asked through a response to open-ended questions to report any post-surgery adverse events to the study coordinator or physician at the 6-week visit and at the subsequent follow-up visits at 6-month intervals. If a serious adverse event, particularly a hospitalization, occurs, the participants will be asked to report that immediately to the study coordinator or physician. All adverse events are captured by the study coordinator on the adverse event logs. Finally, specific pain information is being collected as a part of all follow-up visits to characterize differences in post-operative pain beyond 6 weeks.

The group of measures collected inter-operatively and peri-operatively includes those in the table below. These measures include continuous measures as well binary and ordinal measures. For the

continuous measures, summaries will be presented by treatment arm that include mean levels and standard deviations and linear models with treatment as the primary predictor, controlling for site will be used to test for differences by treatment arm. For the binary and ordinal measures, summaries will included counts and percentages associated with each level of the binary or ordinal measure and Cochran-Mantel-Haenszel statistics and associated p-value with analyses stratified by site will be used to characterize differences in the treatment arms.

The AEs collected through the standard AE form will be summarized using standard contingency tables by treatment arm. These summaries will be provided by individual treatment-emergent AEs, AEs by body system, and AEs by subject. In addition to these general descriptions, specific comparison of risk and differences across the treatment arms will be evaluated for the outcomes listed in the table below.

Summary of Safety V	ariables				
Inter-operative and peri-operative measures					
Variable	Туре	Definition			

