Operative time	Continuous	Obtained directly from peri-operative form			
Blood loss	Continuous	Obtained directly from peri-operative form			
Blood transfusion	Binary	Obtained directly from peri-operative form			
Complications	Ordinal	All complications will be collected and scored on a five- point ordinal scale using the Dindo classification scheme (Dindo, 2004). Each participant will then be classified according to the most severe complication			
Routinely Collected	Adverse Events				
Mesh-related Complications	Ordinal	Mesh related complications: mesh exposure in the vagina or mesh erosion into another organ; note that level of complication will be characterized into based on the following response classification schema: (a) None or non-surgical medical intervention only; (b) Minor or intra-office surgical intervention; (c) Outpatient surgery; (d) Inpatient surgery			
Pelvic infection	Binary	Any incident of pelvic infection will be captured as a Ye response (AE or SAE) to Question 13 in the complication section of the Hospitalization form or Question 14 of the follow-up evaluation form. It will also be captured base on open-ended AE responses with comments indicative pelvic infection.			
Perioperative infection	Binary	A perioperative infection will be captured as a Yes response (AE or SAE) to one or more of Questions 13, 14, 22, 23, 24, or 25 of the Hospitalization form or Questions 15, 16, 17, 18, 19, or 10 of the Post-operative visit form.			

UTI	Binary	A UTI will be captured as a Yes response (AE or SAE) to Question 23 of the Hospitalization form, Question 18 of the Post-operative visit form, or Question 20 or the 6- to 60- Month Study follow-up form or by an event classified as a Urinary Tract Infection based on Preferred terms in the AE form.		
Vaginal infections	Binary	A Vaginal Infection will be captured as a Yes response (AE or SAE) to Question 22 of the Hospitalization form, Question 17 of the Post-operative visit form, or Question 19 or the 6- to 60- Month Study follow-up form or by an event classified as a vaginal infection based on either the preferred term or comments for an event on the AE form.		
Vaginal shortening	Binary	Vaginal shortening will be determined by an event classified as a vaginal shortening based on either the preferred term or comments for an event on the AE form.		

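### SAP Section 10 prespecifies no effect measure or confidence interval for binary and ordinal safety outcomes, and so no upper limit on the mesh exposure rate

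*SAP*

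**What the plan says.** SAP 10.1 sets the general method: "Descriptive p-values comparing the study arms will be provided on most safety table summaries", obtained by "Fisher exact tests if the occurrence of such events is rare and Cochrane-Mantel-Haenszel tests for more common events". No number or rule defines rare.

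SAP 10.2 plans counts and percentages with site-stratified CMH for the binary and ordinal peri-operative measures, linear models for the continuous ones, and contingency tables by arm for adverse events. It adds that "specific comparison of risk and differences across the treatment arms will be evaluated for the outcomes listed in the table below". That table includes mesh-related complications, typed as ordinal with four levels and not restricted to mesh recipients. The lowest level is "a) None or non-surgical medical intervention only".

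Elsewhere, SAP 3.1.2 promises "specific planned secondary analyses and associated hypothesis tests and treatment effect estimates" for the secondary aims, of which safety is the second. SAP 7.7 says "All analyses of secondary outcomes are exploratory in nature; therefore, p-values and confidence intervals are provided for descriptive purposes only", then turns to safety: "All p-values provided for any baseline and demographic characteristics and safety parameters will be for descriptive purposes only". SAP 9.4.3 plans point and interval estimates for the functional outcomes, and SAP 7.4 gives the DSMB point and interval estimates of the important complication rates.

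According to SAP 2, the results also feed a "report on the efficacy and safety of mesh-associated surgery required by the FDA under a 522 letter request".

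**The concern.** Comparing safety is part of the trial's stated primary purpose (SAP 3.1.1), and the results go into a regulatory report on mesh surgery. With about 88 women per arm, a p-value above 0.05 is compatible with both no excess harm and a substantial one; an interval shows which excesses remain plausible. The SAP plans intervals for functional outcomes and for the DSMB but names none in Section 10.

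Mesh complications make the gap sharper. Women in the native-tissue arm receive no Uphold mesh, so a test of equal risk says little about it. A surgeon or regulator needs to know how high the exposure rate could be among women who received the device, and no prespecified output answers that.

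The gap also carries forward. The Protocol's E-SUPeR amendment continues mesh examinations yearly from year 6 to year 10 and ties its analyses to the methods used at 3 and 5 years.

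**Working it through.** The documents give no safety power, precision or detectable rate, so there is no planned figure to reproduce.

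**Inputs.** Arm sizes are 88 (Uphold) and 87 (native tissue), from the table shells in SAP 17. The count of 5 exposures against 0 is an assumption chosen for illustration; neighbouring counts are shown. The Protocol's background section cites an exposure rate of 1.9% from one published series.

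**Fisher, two-sided, 5/88 against 0/87.** With 5 events in 175 women:
- P(all 5 in the Uphold arm) = C(88,5)/C(175,5) = 0.0303
- P(all 5 in the other arm) = C(87,5)/C(175,5) = 0.0286
- Sum: p = 0.059

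**CMH, one stratum, no continuity correction, same data.**
- Expected Uphold events = 5 × 88/175 = 2.514
- Variance = 5 × 170 × 88 × 87/(175² × 174) = 1.221
- Statistic = (5 − 2.514)²/1.221 = 5.06 on 1 df, p = 0.024

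Stratifying over eight assumed equal sites gives p between 0.013 and 0.025, depending on how the events fall. (SAP 7.4 gives eight sites; equal size is an assumption.)

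| Uphold events vs 0 | Fisher p | Unstratified CMH p |
|---|---|---|
| 3 | 0.246 | 0.083 |
| 4 | 0.121 | 0.045 |
| 5 | 0.059 | 0.024 |
| 6 | 0.029 | 0.013 |

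At 4 and 5 events the two tests named in the SAP fall on opposite sides of 0.05.

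**How often p exceeds 0.05 against 0/87.** Fisher needs at least 6 events and CMH at least 4, so the chances are P(X ≤ 5) and P(X ≤ 3) for X ~ Binomial(88, rate).

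| True exposure rate | Fisher | Unstratified CMH |
|---|---|---|
| 1.9% | 99% | 91% |
| 5% | 72% | 35% |
| 8% | 28% | 7% |

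At the cited rate, a p-value would almost never fall below 0.05 by either test.

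**What an interval would show.**
- Exact (Clopper-Pearson) 95% CI for 5/88 = 5.7%: lower limit is the 0.025 quantile of Beta(5, 84) = 1.9%; upper limit is the 0.975 quantile of Beta(6, 83) = 12.8%.
- Upper limit for 0/88: 1 − 0.025^(1/88) = 4.1%.
- Newcombe 95% CI for the risk difference. The Wilson limits are 2.45% to 12.62% for 5/88 and 0% to 4.23% for 0/87. Lower limit: 5.68 − √[(5.68 − 2.45)² + 4.23²] = 0.4 points. Upper limit: 5.68 + (12.62 − 5.68) = 12.6 points.

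**The case against.** The strongest reply is that the SAP does more than print p-values. Counts, percentages and a comparison of risks are planned, effect estimates are promised in general terms for the secondary aims, and SAP 7.7 mentions confidence intervals for secondary outcomes. A reader might infer that safety is compared by p-values alone; the documents do not support that. What stands is that Section 10 names no estimator or interval, and that the safety sentence in SAP 7.7 names only p-values.

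Safety p-values are also labelled descriptive, and the 5% level belongs to the primary efficacy measure. A reader might infer that 5 against 0 would be declared not significantly different. The SAP contains no such rule, and CMH gives 0.024 for the same data.

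A reader might also infer that the lowest mesh level merges unaffected women with conservatively managed exposures. This is not established. SAP 3.2 defines adverse-event risk as the proportion of participants with an event, mesh exposure or erosion included, and the Protocol treats the four levels as grading the intervention given. The no-event category could be clearer, but no loss of cases is shown.

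Finally, midurethral slings are allowed without restriction by arm (Protocol J.2), and the documents do not say whether sling exposure counts as a mesh complication. Zero risk in the native-tissue arm therefore holds for Uphold mesh only. A mesh p-value is likely but not explicit: SAP 10.1 says most tables, and no visible shell has a mesh row.

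It is true that exact limits can be worked out from reported counts. That is no reason to leave them out of the plan.

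**Conclusion.** The point holds as a gap in specification with a cheap remedy. For the final comparison of binary and ordinal safety outcomes, SAP Section 10 names no effect measure or interval, and the undefined switch between Fisher and CMH can move a result across 0.05 (0.059 against 0.024 for 5/88 vs 0/87). No upper limit on the Uphold exposure rate is prespecified: it would be 12.8% after 5/88 and 4.1% after 0/88. These figures rest on the shell sample sizes, assumed event counts and, for the CMH value, an unstratified test. The point does not depend on safety p-values being read as formal tests. Intervals would not raise the trial's power to detect harm; they would show how much harm the data leave possible.

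**What to change.** In SAP 10.1 and 10.2, report for each listed binary safety event the risk in each arm and the risk difference with a 95% CI, by Newcombe or Miettinen-Nurminen for example. Keep p-values as descriptive only and state when Fisher and when CMH applies.

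For Uphold mesh exposure or erosion, make the main result the proportion among women who received Uphold, with an exact 95% CI. The SAP's safety population, grouped by treatment received, already supplies that denominator. Count every exposure, including those managed without surgery, and report any sling-mesh exposure separately by arm.

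The cost is SAP wording and extra table columns, with no new data. The downside is wide intervals, so the safety statements will be less reassuring.
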